4.2.6 Post-hospital Procedures

No procedures are required after discharge from the hospital (except for a telephonic questionnaire conducted at 4, 8, and 12 months of age – see 4.2.7 below).

4.2.7 Additional Follow-up Examinations and/or Questionnaires

The subject's pulmonary and nutritional status will be initially recorded at discharge. Subsequently, a study questionnaire evaluating breathing outcomes and nutritional status will be administered at 4, 8, and 12 months of age by a telephonic interview. This questionnaire is a modification of the questionnaire used for the SUPPORT trial. (Stevens, Finer et al. 2014)

SECTION 5. ANALYTICAL PLAN

5.1 SAMPLE SIZE AND POWER ESTIMATES

Sample Size: In the case series describing the effect of milrinone among neonates with CDH, baseline OI (mean \pm SD) was 10.6 ± 5.6 , and improved to 7.9 ± 6.2 and 5.1 ± 2.6 at 12-24 h and at 48-72 h, respectively (Patel 2012). Assuming that children receiving placebo will have no additional change in OI (mean change in OI = 0 at 24 hours), that children receiving milrinone will improve to a mean OI of 6.0 (a mean change in OI of 4.6) at 24 hours, and that the standard deviation of the change from baseline OI at 24 hours in each group is 6.2, 33 subjects in the control group and 33 subjects in the milrinone group would have 84% power to detect this difference with a two-sided alpha of 0.05 (note that 6.2 is a conservative standard deviation estimate, as data from the Patel et al study indicate that the standard deviation for change from baseline in OI at 24 hours may be as low as 1.5). Phrased differently, if both the control and treatment OI's were to change, for any given difference in OI, the sample size would be sufficient to detect an effect size of 0.7 with a power of 84%. The sample size will be sufficient to provide estimates of adverse event rates in the treatment group. The following table provides the 95% confidence intervals for observed adverse event rates varying from 6% to 49% for a sample size of 33 subjects.

Table 8. Confidence Intervals for Observed adverse event rates.

Point estimate	0.06	0.09	0.21	0.30	0.39	0.49
95% CI	(0.007, 0.2)	(0.02, 0.24)	(0.09, 0.39)	(0.16, 0.49)	(0.23, 0.59)	(0.31, 0.66)

Within the NRN centers, approximately 36% of neonates with CDH who are \geq 36 weeks PMA require ECMO. In a selective population (isolated CDH with OI \geq 10), we estimate that the risk of ECMO or death prior to discharge (or by day 120) will be approximately 40%. A sample size of 33 in the placebo arm would provide a 95% confidence interval for this estimate of (26%, 58%). The precision of estimates for outcome rates in the treatment group can be seen in table 8.

Limitations:

- (a) This study is not powered to compare rates of the outcome of death or ECMO between groups. To detect a reduction of 10% (from 40% incidence of death/ECMO in control arm to 30% incidence in the milrinone arm), with a 1:1 ratio of treatment and control subjects, a power of 0.8 and an alpha value of 0.05, we would require 376 subjects in each arm.

(b) The study is also not powered to compare a sicker cohort of CDH patients similar to that evaluated in the CDH NINOs study (1997). The patients in CDH NINOs study had an OI of approximately 45 with standard deviations of 16.3 and 14.5 in control and treatment groups respectively. Such a cohort will require a sample size of 207 patients in each arm to achieve the primary outcome outlines in the current protocol. We intend to enroll patients early at a lower OI (or OSI).

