3.1. PRIMARY OUTCOME

The primary outcome is the oxygenation response, as determined by change in OI (or OSI if no arterial blood gas is available) at 24h after initiation of study drug. In patients that require ECMO or die prior to completion of 24h from the initiation of the study drug, the last OI (or OSI, if no arterial blood gas is available) prior to initiation of ECMO or death will be used for analysis. A difference in OI of 4 points in mean change from baseline OI at 24 h between experimental and control groups will be considered significant (OI increased by 4 ± 14.8 in the control group and decreased by 2.7 ± 23.4 following iNO in the CDH NINOS study (1997). In the Patel study, following milrinone infusion, OI decreased by 2.7 ± 1.7 from baseline by 12-24 h and 5.5 ± 3.2 by 48-72 h; the mean change in OI of both these time points is a decrease by 4.1 ± 1.5 (Patel 2012)). This outcome will be used for sample size calculation. Although a decrease in OI by 4 points may not be clinically significant, this number is based on the only published case series showing the use of milrinone in CDH. In patients without an arterial line (or if the line is lost), oxygen saturation index (OSI) will be calculated using a preductal oximeter. (Rawat, Chandrasekharan et al. 2015)

Oxygenation index (OI) = Mean airway pressure (cm H₂O) x FIO₂ x 100 ÷ PaO₂ (mm Hg)

Oxygen saturation index (OSI) = Mean airway pressure (cm H₂O) x FIO₂ x 100 ÷ SpO₂ (%)

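### Sections 3.1 and 5.1: the 84% power for 4.6 OI points is correct, but the 4 points named in 3.1 have about 73%, and four nearby figures need correcting

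*Combined protocol and SAP*

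**What the plan says.** Section 5.1 assumes no mean change in OI on placebo and a fall from 10.6 to 6.0 on milrinone, "a mean change in OI of 4.6". With an SD of change of 6.2 in each arm, 33 infants per arm and two-sided alpha 0.05, it states 84% power. It then restates this as a general claim, meant to hold whatever the two arms do, namely that "the sample size would be sufficient to detect an effect size of 0.7 with a power of 84" per cent.

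Section 3.1 says: "A difference in OI of 4 points in mean change from baseline OI at 24 h between experimental and control groups will be considered significant". After citing results from two earlier studies it adds: "This outcome will be used for sample size calculation". From the milrinone case series it reports mean falls in OI of 2.7 (SD 1.7) by 12–24 h, 5.5 (SD 3.2) by 48–72 h, and 4.1 (SD 1.5) for the two time points averaged.

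On the SD, section 5.1 says "note that 6.2 is a conservative standard deviation estimate", and that on the case-series data "the standard deviation for change from baseline in OI at 24 hours may be as low as 1.5".

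On the rate of ECMO or death, assumed to be about 40%, it says: "A sample size of 33 in the placebo arm would provide a 95% confidence interval for this estimate of (26%, 58"%). Table 8, in the same section, gives (0.23, 0.59) for an observed adverse event rate of 0.39 in 33 subjects.

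**The concern.** Two places describe the difference the trial is built around, and they give different numbers. If 4 points is the difference of interest, the 84% does not apply to it, and the protocol nowhere states the power that does. A reader facing a non-significant primary result would then assume a 16% chance of having missed the named difference, when at SD 6.2 it is about 27%.

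The effect-size sentence adds to this. It is offered as holding for any difference in OI, so it is the sentence most likely to be reused on its own, and at 0.7 the stated power is too high.

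The interval for ECMO or death describes how precisely the control-arm rate will be known, and specific aim 4 wants that rate for planning a definitive trial. The printed interval is narrower than it should be, and the error is at the low end.

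**Working it through.** **Power.** Inputs from section 5.1: 33 per arm, SD of change 6.2, two-sided alpha 0.05. Method: unadjusted two-sample t-test, noncentral t with 64 degrees of freedom and noncentrality d × √(33/2) = 4.062 d, where d = difference / SD.

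| Difference | d | Noncentrality | Power (t) | Power (normal approx.) |
|---|---|---|---|---|
| 4.6 (section 5.1) | 4.6/6.2 = 0.742 | 3.01 | 84.3% | 85.4% |
| effect size 0.74 | 0.74 | 3.01 | 84.1% | 85.2% |
| effect size 0.7 (restatement) | 0.70 | 2.84 | 80.0% | 81.2% |
| 4.1 (case-series average) | 4.1/6.2 = 0.661 | 2.69 | 75.4% | 76.6% |
| 4 (section 3.1) | 4/6.2 = 0.645 | 2.62 | 73.3% | 74.6% |

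The first row reproduces the plan's 84%. The effect size with 84% power at 33 per arm is 0.738, or 0.74 to two decimals. Neither method gives 84% at 0.7.

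**Adjustment for HRF severity.** The primary model in section 5.4 adjusts for the HRF stratum, which could reduce the residual SD to 6.2 × √(1 − R²). The documents give no R², so these values are assumptions. For 4 points, R² of 5% gives 75% power, 10% gives 78% and 20% gives 82%. About 24% would be needed to reach 84%.

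**Interval for about 40% of 33.** The exact (Clopper-Pearson) limits for x events in n are the 2.5% quantile of Beta(x, n − x + 1) and the 97.5% quantile of Beta(x + 1, n − x).

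- x = 13 (39.4%): Beta(13, 21) and Beta(14, 20) give (22.9%, 57.9%).
- x = 13.2 (exactly 40%, not a whole count): (23.4%, 58.5%; the upper limit before rounding is 58.45%).
- Both round to (23%, 58%).
- Other methods for 13/33: Wald (22.7%, 56.1%), Wilson (24.7%, 56.3%), Agresti-Coull (24.7%, 56.4%), Jeffreys (24.2%, 56.4%). None gives 26% with 58%.
- Width: printed 58 − 26 = 32 points; exact 57.9 − 22.9 = 35 points.

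**Table 8 by the same exact method, n = 33.**

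| Events | Exact | Printed |
|---|---|---|
| 2 | (0.007, 0.202) | (0.007, 0.2) |
| 3 | (0.019, 0.243) | (0.02, 0.24) |
| 7 | (0.090, 0.389) | (0.09, 0.39) |
| 10 | (0.156, 0.487) | (0.16, 0.49) |
| 13 | (0.229, 0.579) | (0.23, 0.59) |
| 16 | (0.3080, 0.6646) | (0.31, 0.66) |

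Five of the six intervals reproduce. In the fifth row the upper limit should be 0.58.

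**The SD of 1.5.** Table 5 has OI data for five infants. Falls from baseline:

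- 12–24 h: 2.4, 1.2, 1.6, 2.75, 5.5; mean 2.69, SD 1.69.
- 48–72 h: 9.8, 7.8, 4.7, 1.75, 3.7; mean 5.55, SD 3.23.
- Average of the two: 6.1, 4.5, 3.15, 2.25, 4.6; mean 4.12, SD 1.48.

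This agrees with section 3.1: 1.7 is the SD at 12–24 h, and 1.5 is the SD of the averaged change. Section 5.1 attaches 1.5 to 24 hours.

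**The case against.** The strongest reply is that the calculation that set the sample size is correct and the rest is presentation. Much of that stands.

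- The 0.7 is evidently 0.742 to one decimal, and the sentence presents itself as a rewording of the calculation before it. The remedy is one more digit. The sentence is still wrong as printed.
- The 4.6 is not without derivation: it is 10.6 less an assumed 6.0, and 6.0 lies between the case series' 7.9 and 5.1. Only the choice of 6.0 is unexplained.
- Section 3.1 ties the outcome to the sample size, not expressly the 4 points, and a difference regarded as important need not equal the design alternative. The wording is ambiguous, which is a reason to reconcile it.
- The 1.5 enters no calculation, and 1.7 is also far below 6.2.
- The misprinted interval feeds no decision. The 376 per arm for a definitive trial uses the 40% point estimate, and aim 4 will use the observed rate. Likewise, a null result is best read from the observed confidence interval for the treatment effect, not from planning power.

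A reader might infer more than the documents support:

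- **That the trial is undersized and needs 43 per arm**, the number giving 84% for 4 points at SD 6.2. That follows only if 4 points was the design target, which 3.1 does not clearly say; under 5.1's own inputs 33 per arm is right.
- **That the 207 per arm in limitation (b) shows 4 points was the true target.** The number does follow from 4 points, SD 14.5 and 80% power: 2 × (1.96 + 0.8416)² × 14.5² / 4² = 206.3. But the difference and power used are not stated there, and two SDs are, so this is a reconstruction and settles nothing.
- **That section 5.1 gives two intervals for one quantity.** The text concerns ECMO or death on placebo; the Table 8 cell concerns adverse events. They are separate slips.
- **That 6.2 is a wrong input.** It equals the SD of OI values at 12–24 h quoted in the same paragraph, but the text does not say it came from there. That is missing detail, not a demonstrated error.

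**Conclusion.** The point holds as a set of corrections to the text and is minor. The 84% for 4.6 points at SD 6.2 is correct, and n = 66, the design and the analysis are unaffected.

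The item with most bearing on interpretation is the unreconciled 4 versus 4.6: power is about 73% for the smaller difference, 11 points below the stated figure. This rests on SD 6.2 in both arms and an unadjusted t-test; adjusting for HRF severity would raise it by an amount the documents do not allow one to fix.

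The other corrections are firm. Effect size 0.7 has 80% power, not 84%. The lower limit for about 40% of 33 is about 3 points too high against the exact method that Table 8 otherwise follows. One Table 8 limit is off by 0.01. The 1.5 is mislabelled by section 3.1's own account, without effect on the power.

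**What to change.** Keep n = 66 and make four edits:

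1. Reconcile the 4 points in section 3.1 with the 4.6 in section 5.1. If 4.6 remains the design assumption, say why a mean OI of 6.0 at 24 h was chosen and what role the 4 points play. State that 4 points at SD 6.2 has about 73% power by an unadjusted t-test, before any gain from adjusting for HRF severity.
2. In the restatement, write 0.74 for 84% power, or 80% power for 0.7.
3. Change the interval for the 40% rate to about (23%, 58%) and name the exact method. Change Table 8's upper limit for 0.39 from 0.59 to 0.58.
4. Replace 1.5 with 1.7 as the SD of change at 12–24 h, or label 1.5 as the SD of the change averaged over the two time points.

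The cost is a few sentences in sections 3.1 and 5.1 and one table cell. The one drawback is that the power shown for 4 points looks less favourable than the 84% now printed.

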5.2 AVAILABLE POPULATION

Available population/duration of the study: There are currently no protocols involving term/late preterm infants with CDH in the NRN (except the observational study for early-onset sepsis which does not interfere with this protocol). The International CDH study group (not associated with NRN) comprises of approximately 75 centers. These centers enrolled 300 babies into the registry in 2009. The number of babies with CDH within the NRN per year was approximately 170/ year from 2011 to 2012. More recent data obtained from the NRN grant applications shows a higher number (approximately 227/ year). Information about the number of patients available within the NRN during 2011 and 2012 is given in table 9.

Table 9. Infants with congenital diaphragmatic hernia in the Neonatal Research Network

	2011	2012	Average
Total CDH admissions	175	162	169
CDH \geq 36 0/7 week PMA	142	133	138 (82%)
Inhaled NO in the preoperative period among CDH \geq 36 0/7 weeks PMA	71	72	72 (43%)
Other medications used in the preoperative period among CDH \geq 36 0/7 weeks PMA			
Milrinone	17	29	23 (17%)
Sildenafil	29	25	27 (20%)
Flolan ® (inhaled epoprostenol)	8	9	9 (6%)
Flolan ® (intravenous epoprostenol)	6	3	5 (3%)
Alprostadil (intravenous PGE1)	6	5	6 (4%)
Epinephrine	2	1	2 (1%)
ECMO among all CDH	59	56	58 (34%)
ECMO among CDH \geq 36 0/7 weeks PMA	51	48	50 (36%)
Survival to discharge			
- all CDH	111	117	114 (68%)
- CDH \geq 36 0/7 weeks PMA	94	101	98 (71%)
Concern regarding use of iNO in CDH	Yes – 8; No – 11		
Primary physician managing pulmonary vasodilator therapy			
Surgeons – 4; Neonatologists – 10; Joint (surgeons + neonatologists – 3); PICU – 1			

[figure not shown]
Duration of study (figure 7):

- (i) There are approximately 138 babies with CDH \geq 36 weeks PMA per year within the NRN.
- (ii) Eighty percent of CDH patients have isolated CDH without other major anomalies ($138 \times 0.8 = 110$ patients).
- (iii) Approximately 35% of these patients do not meet inclusion criteria ($OI < 10$ mild disease or severe disease and/or hemodynamic instability): $110 \times 0.65 = 71$ patients (based on preliminary calculations using 11 patients in Buffalo and 116 patients from Milwaukee).
- (iv) Refusal to participate in the study (parents and/ or physician not consenting to the study or are cared by another service that does not want participation in a trial) – 50%: $71 \times 0.5 = 35$ patients per year or 66 patients in approximately 2 years (figure 7).

5.3 PROJECTED RECRUITMENT TIME

We anticipate that it will take 24 to 36 months for enrollment and an additional year for administering the pulmonary/ nutritional status questionnaire. It will take approximately 48 months for the completion of this pilot study. Infants with CDH are a special population with high morbidity and mortality. We anticipate that enrollment might be slower than expected.

Figure 7.
Outline of the
study

5.4 STATISTICAL ANALYSIS PLAN

Baseline data will be collected prior to randomization including gestational age, side of the diaphragmatic hernia, birth weight, mode of delivery and arterial blood gas parameters (oxygenation index-OI) and/or pulse oximetry data (oxygen saturation index-OSI). Data from a baseline clinical echocardiogram is recorded (if performed prior to study drug initiation or within 2h of initiation of study drug). During the infusion of study drug, arterial blood gas parameters and hemodynamic data (blood pressure, heart rate and echocardiography results) will be recorded. After completing the study infusion, surgical details, and mortality information will be collected. Among survivors, respiratory and nutritional status at discharge and at 4, 8 and 12 months of age will be collected.

Data will be presented as mean \pm SD for normally distributed variables and as median and ranges (with percentiles) for non-normally distributed data. All analysis will be by intention-to-treat. Baseline characteristics will be compared between treatment groups using chi-square and Fisher's exact test for discrete variables and t-test and ANOVA for continuous variables. The primary outcome, difference from baseline OI at 24 h, will be compared between treatment groups using a general linear model adjusted for the stratification factor of HRF severity. Other continuous outcomes will be analyzed similarly. Models for longitudinal outcomes such as oxygenation and vasoactive inotrope scores (short-term) and nutritional and pulmonary outcomes at 12 months (long-term) will include the effect of time, the interaction between time and treatment, and random effects to account for the correlation between measures taken on the same individual over time. Categorical outcomes will be analyzed using analogous generalized linear models. Cox regression models (with adjustment for HRF severity) will be used to plot proportion of responders who survive without ECMO against survival time in hours. Analyses may adjust for clinical site if treatment assignments are severely imbalanced for some sites provided that it is computationally feasible to do so. The potential influence of baseline measures such as time of diagnosis – antenatal vs. postnatal, side of the defect, and gender on pulmonary and nutritional outcome will be explored through the use of additional models similar to those described above.

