inotrope score > 30; Vasoactive Inotrope score = dose of dopamine in $\mu\text{g}/\text{kg}/\text{min}$ + dose of dobutamine in $\mu\text{g}/\text{kg}/\text{min}$ + 100 X epinephrine dose in $\mu\text{g}/\text{kg}/\text{min}$ + 100 X norepinephrine dose in $\mu\text{g}/\text{kg}/\text{min}$ + 100 X phenylephrine dose in $\mu\text{g}/\text{kg}/\text{min}$ + 10000 x vasopressin dose in $\text{U}/\text{kg}/\text{min}$) two hours after initiation of study drug. Infusion will be continued until the OI decreases to < 7 (or OSI < 3.5 if no arterial blood gas is available). The study drug will be continued during surgery and if the patient requires either veno-arterial or veno-venous extracorporeal membrane oxygenation (VV-ECMO or VA-ECMO) if permitted by the clinical team. The maximum duration of study drug infusion is 72 h. After 70 h (if the patient is on 0.66 $\mu\text{g}/\text{kg}/\text{min}$ or 72h if the patient is on 0.33 $\mu\text{g}/\text{kg}/\text{min}$) of study drug infusion (or earlier if two consecutive OIs at least one hour apart are < 7 or OSIs < 3.5 if no arterial blood gas is available), the infusion rate of the study drug is weaned and subsequently discontinued. Data from a maximum of 4 echocardiograms, **if performed for clinical indications will be recorded**, (a) first echocardiogram, preferably prior to onset of study drug or within 6 hours of initiation of study drug, (b) second echocardiogram, 6 – 36 h after initiation of study medication (c) third echocardiogram, 36 h after initiation of study medication but prior to completion or discontinuation of study-drug and (d) first echocardiogram after completion of the study drug.

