3.2. SECONDARY OUTCOMES

- (i) Oxygenation response at 24 h after initiation of study drug assigning a minimum OI of 40 or OSI of 20 (if no arterial blood gas is available) for subjects that need ECMO or die after initiation of study drug infusion but prior to 24h of study-drug infusion. In this analysis if the patient's OI is 30 (or OSI of 15) and is cannulated for ECMO due to hemodynamic instability, he/she will be assigned an OI of 40 (or OSI of 20). However, if the OI prior to ECMO is 47 (i.e., > 40), the higher number (47) will be used for analysis of this secondary outcome.
- (ii) Oxygenation index at 48 and 72 h after initiation of study drug (or OI/OSI at the time of initiation of ECMO or immediately prior to death, for infants placed on ECMO or died before these time points),
- (iii) Change in echocardiographic findings – velocity of tricuspid regurgitation, left ventricular ejection fraction, position of the interventricular septum and direction of shunt at the PDA and PFO level – prior to and 24-72h after starting the study

medication. This outcome will be available only for those infants who have a pre-study drug echocardiogram and a second echocardiogram between 24-72 h after initiation of study drug. These data will be extracted from echocardiograms performed for clinical indications.

- (iv) Vasoactive Inotrope score and systemic blood pressure
- (v) Area under the curve for inspired oxygen after initiation of the study drug over the first 72 hours of study-drug infusion (or prior to ECMO or death, whichever is earlier) (Note: inspired oxygen and ventilator data from 4 time points per day – every 6 hours will be recorded to calculate area under the curve),
- (vi) If subsequent to the study drug, any additional inotrope or pulmonary vasodilator is used (such as iNO), we will evaluate the oxygenation response to these agents. If inotropes or vasodilators were used prior to the initiation of study drug, similar values will be recorded. The OI (or OSI) and $\text{PaO}_2/\text{FiO}_2$ ratio prior to and after initiation of the inotrope / vasodilator are recorded (these data are recorded at 6 hour intervals; the date and time of initiation of individual inotropes and vasodilators is recorded). The change in OI (or OSI) and $\text{PaO}_2/\text{FiO}_2$ ratio in response to these agents is evaluated as a continuous variable and arbitrarily classified into responders, partial responders and non-responders similar to prior trials (1997, 1997).

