2. One complete blood count (CBC) with a platelet count of $> 80,000/\text{mm}^3$ on the most recent evaluation prior to enrollment is required for randomization. This CBC may be drawn after one or multiple platelet transfusions.
3. The use of therapies such as sedation, analgesia, paralysis, surfactant, high frequency ventilation, iNO, pressors, inhaled prostaglandins (including PGE₁ and prostacyclin) and steroids are permitted at the discretion of the clinical team (and/or based on written center guidelines – a copy of each center's guidelines, if available, will be collected prior to enrollment).
4. Infants with CDH as part of a congenital syndrome that does not cause cardiopulmonary or renal compromise (e.g., rib cage anomalies, renal dysplasia) can be included in the study. Infants with trisomy 21 and CDH without cyanotic heart disease or kidney disease affecting renal function may be included in this trial.

5. A baseline echocardiogram (if ordered for clinical indications) prior to initiation of study drug or within 6 hours of initiation of study-drug is preferred as a baseline study. However, consenting, randomization and preparation of study drug by the pharmacy may proceed without an echocardiogram. It is not necessary to wait for the “official” results of the echocardiogram to commence study drug (unless there is a high suspicion for cyanotic congenital heart disease).

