Subject specimens: Information about blood counts, imaging and blood gases will be obtained from blood draws conducted for the purpose of clinical care. No additional blood work will be performed for the purpose of research.

Echocardiography: Data from a maximum of 4 clinical echocardiograms will be recorded. No additional echocardiograms will be performed for the purpose of this study. To estimate the secondary outcome of improvement in cardiac function and pulmonary hypertension, data from at least two echocardiograms will be obtained if available – the first echocardiogram preferably prior to initiation of the study drug. If echocardiogram is not performed prior to study drug initiation, study drug may be initiated.

If clinical echocardiograms are obtained during the study drug infusion, data from the clinical echocardiogram closest to 24 hours after study drug infusion is used to calculate the secondary outcome of change in echocardiographic findings. If a third echocardiogram is obtained close to 72 hours after initiation of study drug, data from this study will be recorded. In addition, data from any other echocardiograms obtained for clinical purposes after completion of study drug will be recorded (maximum of 4 echocardiograms).

Cranial ultrasound: As mentioned previously, an initial cranial ultrasound is obtained prior to initiation of study drug or within 4 hours of commencement of the study drug. A second cranial ultrasound is obtained preferably within 24 hours (maximum within 96 hours) of completion of the study drug. Both these cranial ultrasounds are covered by the study budget. Additional head imaging may be performed based on clinical indications but are not covered by the study budget. If the patient has a screening ultrasound that demonstrates intracranial hemorrhage

(as outlined in the exclusion criteria) prior to starting the study-drug, the patient is not randomized. In this case, only one screening cranial ultrasound is covered by the study budget.

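### Secondary outcome (iii), the echocardiographic change in aim 1, has contradictory rules for which baseline and follow-up echo to use

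*Combined protocol and SAP*

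**What the plan says.** Five places bear on this outcome.

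- **Section 3.2(iii)**, repeated in the synopsis list of secondary outcomes, says who contributes: "This outcome will be available only for those infants who have a pre-study drug echocardiogram and a second echocardiogram between 24-72 h after initiation". Specific aim 1 (Section 2.2) uses the same 24-72 h span.
- **Section 4.2.5, Echocardiography**, describes how this outcome is estimated. It asks for a first echo before study drug only as a preference. Where echoes are done during the infusion, "data from the clinical echocardiogram closest to 24 hours after study drug infusion is used to calculate the secondary outcome". No 24 h lower limit is given.
- **Section 5.4** records a baseline clinical echo done before study drug starts or "within 2h of initiation of study drug".
- **Section 4.1.2, Note 5** says an echo "prior to initiation of study drug or within 6 hours of initiation of study-drug is preferred as a baseline study".
- **The synopsis, Study Intervention/Methods**, describes the first recorded echo as "preferably prior to onset of study drug or within 6 hours of initiation of study drug". It puts the second recorded echo at 6-36 h.

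Section 4.2 separately defines baseline in general as the 30 minutes before study drug starts. No section says which rule takes precedence for the echo outcome.

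**The concern.** Both ends of the change score depend on the section followed. A first echo shortly after drug start is a baseline in some sections and disqualified in another. A second echo before 24 h is the one to use in one section and inadmissible in another.

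Two things are at stake. First, an echo taken after drug start is an on-treatment measurement. If it serves as baseline and milrinone has already begun to act, part of the effect is subtracted from the milrinone arm and nothing comparable from placebo. Second, rules that disagree leave room to choose among them once the data are visible. Echo change appears in the primary hypothesis (Section 2.1) as well as in aim 1, so readers are likely to give it weight even though it is a secondary outcome.

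**Working it through.** The plan states no sample size, power or expected effect for the echo outcome, so there is no figure to reproduce. The check is to apply each section's rule to the same echo times, in hours from study drug start.

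**Baseline**

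| First echo at | 3.2(iii): before drug only | 5.4: up to 2 h | 4.1.2 Note 5 and synopsis: up to 6 h |
|---|---|---|---|
| 3 h before start | accepted | accepted | accepted |
| 1 h after start | rejected | accepted | accepted |
| 4 h after start | rejected | rejected | accepted |

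**Follow-up, infant with echoes at 18 h and 40 h**

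- Section 4.2.5, infusion still running: distances from 24 h are |18 − 24| = 6 h and |40 − 24| = 16 h. The 18 h echo is used.
- Section 3.2(iii): 18 lies outside 24-72 and 40 lies inside. The 40 h echo is used.

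With an 18 h echo alone, the infant has an outcome under 4.2.5 and none under 3.2(iii).

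**Dependence on infusion length.** The 4.2.5 rule covers echoes obtained during the infusion. The same section ends the infusion early once two OI values at least an hour apart fall below 7 (OSI below 3.5 without arterial gas). An infant who stops before 24 h and has an echo at 30 h qualifies under 3.2(iii), but that echo is not covered by the 4.2.5 rule. Selection under 4.2.5 can therefore depend on response to treatment.

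**Could an echo in the first 6 h already reflect drug?** Section 2.3.3 reports that neonates given no loading dose reach half of steady-state concentration by 2 h. The planned infusion has no loading dose, and its rate increase falls at 2-4 h, inside the 6 h allowance. Early exposure is thus expected on the plan's own figures. Whether echo measures move that early in CDH is not shown.

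**The case against.** The strongest reply is that only Section 3.2(iii) and its copy in the synopsis define the outcome. Section 5.4 and the synopsis describe what is recorded, and Note 5 states a preference about timing. On that view the baseline is already pre-drug, and 4.2.5 merely chooses among echoes that fall within 24-72 h.

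Part of this stands. The 6-36 h slot is a recording window and does not define the outcome. The 2 h and 6 h limits would be harmless if the plan said that such echoes are excluded from outcome (iii). Section 4.2.5 can be read as working inside 24-72 h.

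The reply fails on 4.2.5 itself. That section also says how this outcome is calculated. It makes the pre-drug echo a preference and does not mention the 24-72 h window. Its time reference is also unclear, since it could mean the start or the end of infusion. A harmonised reading is possible, but the text does not require it.

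A reader might also infer that most second echoes are in dispute, because 18 of the 30 hours in the 6-36 h slot precede 24 h (18/30 = 60%). The documents do not support this. The calculation treats a recording slot as an outcome rule and assumes evenly spread echoes, for which there are no timing data. It also counts echoes, not infants: an infant with an early echo may have a later one that qualifies.

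**Conclusion.** The contradiction holds at the level of the outcome definition: 3.2(iii) and 4.2.5 can select different echoes from the same infant. The baseline limits of 2 h and 6 h also disagree with each other and with 3.2(iii).

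Its size cannot be computed. Echoes are done only for clinical indications, and the plan gives no distribution of their timing.

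It would be tempting to conclude that the milrinone effect will be biased toward zero. That goes too far. The bias needs two conditions, that on-drug echoes are actually used as baseline and that milrinone changes the echo measures within the first hours. Neither is established.

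The point is minor. The primary outcome is change in OI/OSI, and neither it nor the 33 infants per arm depends on this rule. It is still worth correcting, because the repair is almost free and removes a choice that could otherwise be made after seeing the data.

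**What to change.** Before unblinding, state one analysis rule for outcome (iii), consistent with Section 3.2(iii) and aim 1:

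- **Baseline:** the last echo before study drug starts.
- **Follow-up:** the echo closest to 24 h after the start of study drug, within 24-72 h, whether or not the infusion is still running.
- **Echoes at 0-6 h after start:** recorded and listed separately, labelled as not baseline for this outcome.

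Use this wording in 3.2(iii), 4.2.5, 5.4, 4.1.2 Note 5 and the matching synopsis text (Study Intervention/Methods and secondary outcomes). Say how the echo baseline relates to the general 30-minute definition in Section 4.2, and whether there is a look-back limit, since infants may enrol up to 7 days of age.

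No new echoes or data are needed. The cost is that infants whose only first echo is on drug, or whose only follow-up echo precedes 24 h, leave this secondary outcome. Report their number by arm.
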